1.2.1.3 Rationale for the Sub-protocol in Rheumatoid Arthritis

Rheumatoid arthritis is a chronic disease affecting 0.5 to 1.0% of the population in which diarthrodial (synovial) joints become inflamed, usually with a bilateral symmetric pattern, and with a high incidence of damage and disability. RA is a systemic disease, and manifestations may include constitutional symptoms such as fatigue, fever and malaise, vasculitis, cardiovascular complications, ocular involvement, pulmonary interstitial disease, and widespread nodulosis. Patients with RA have a reduced life span which correlates with disease severity, and increased levels of cytokines such as TNF- α , IL-1 and IL-6, circulating ICs, RF, and anti-citrullinated protein antibodies (ACPAs). RF

Despite recent progress in RA therapy with a number of approved targeted biologics in the United States (US) and Europe, ¹² unmet medical needs remain. ²⁴ First, many agents approved for RA exhibit significant safety concerns, including risk of tuberculosis (TB) and other serious infections, malignancies, and gastrointestinal perforation. Second, many patients are only partial responders to current available therapies, and true remission is achieved by only a minority of patients (< 10% in many series). Third, current treatments have toxicities that lead to frequent drug discontinuation. In addition, the destructive process of RA cannot be halted in all patients, and new drugs that reduce osteoclast-mediated bone loss and inflammation may offer unique benefits to patients with RA. ²⁵

ICs containing IgG play a critical role in the immunopathology of many immune-mediated disorders. In RA, ICs are present in the joints and act on synovial macrophages to drive the production of the cytokines, chemokines, and matrix metalloproteinases (MMPs) that are critical in mediating disease pathology. Expression of Fc γ RIIa and Fc γ RIIIa are increased in monocytes and macrophages of patients with RA,^{26, 27, 28} and produce higher levels of TNF α and MMPs than healthy controls.²⁶

Activating Fcγ receptors are also important in the activation of monocyte-derived dendritic cells.²⁹ Genome-wide association studies have shown FcγRIIIa to be associated with RA susceptibility,³⁰ and murine models of RA such as the collagen-induced arthritis (CIA) model have demonstrated a role for activating Fcγ receptors in disease pathogenesis.^{31,32} BTK is highly expressed in myeloid lineages and regulates signaling pathways leading from the binding of ICs to FcγRIIIa and FcγRIIa to expression of pro-inflammatory cytokines, chemokines, and cell adhesion molecules.^{5,6,7,33,34} BTK also mediates FcγRI signaling in mast cells and basophils although the role of these pathways in RA is not well established. However, IgE ACPAs have been identified in patients with RA,¹⁰ and the number of activated mast cells may be increased in synovial tissue and have been correlated with disease activity.^{8,9,11} Thus, inhibition of BTK could have therapeutic benefit on a variety of immunopathogenic features of RA.

Lastly, BTK inhibition could potentially counter the bone damage in RA through its role in mediating RANK-dependent osteoclastogenesis.^{35, 36}

The RA sub-protocol of this study will help determine if branebrutinib is biologically active and effective in the treatment of RA (see Section RA 4.4).

In addition, the safety and efficacy of switching from branebrutinib or PBO to abatacept (also named BMS-188667 and OrenciaTM; referred to hereafter as abatacept) will also be evaluated.

1.3 Master Protocol: Overall Research Hypothesis

[figure not shown]
The processes targeted by BTK inhibition are shared pathogenic molecular mechanisms of multiple immune-mediated diseases. Treatment with branebrutinib (BMS-986195), an oral, highly selective, irreversible inhibitor of BTK, may provide clinical benefit in the treatment of the immune-mediated diseases SLE, pSS, and RA.

Clinical Protocol BMS-986195

1.4 Master Protocol Study Design

This Master Protocol with 3 sub-protocols is a double-blind, placebo-controlled multicenter study to assess the effect of branebrutinib (BMS-986195) treatment in subjects with SLE (SLE sub-protocol), pSS (pSS sub-protocol), and RA (RA sub-protocol). In the RA sub-protocol, the safety and efficacy of switching from branebrutinib or PBO to abatacept, which will be administered at a dose of 125 mg subcutaneously (SC), once weekly (QW), will also be evaluated. Enrollment in each sub-protocol will be concurrent.

Figure 1 Master Protocol Study Design

All Sub-protocols 24 Week Treatment Period

* Time point for Primary end point

pSS = primary Sjögren's syndrome; QD = once daily; R = randomization ratio; RA = rheumatoid arthritis; SLE = systemic lupus erythematosus

1.4.1 Master Protocol: Study Population

- The study population will include male and female subjects aged 18 (or age of majority) to 75 years inclusive at screening. Subjects must have active SLE, moderate to severe pSS, or moderate to severe adult-onset RA.
- Approximately 185 subjects will be randomized in the study (60 subjects in the SLE sub-protocol, 45 subjects in the pSS sub-protocol, and 80 subjects in the RA sub-protocol).
- For the SLE and pSS sub-protocols, there will be a 24-week double-blind placebo-controlled treatment period in which subjects will receive branebrutinib 9 mg or placebo once daily (QD). For the RA sub-protocol, there will be a 12-week double-blind PBO-controlled treatment period in which subjects will receive branebrutinib 9 mg or branebrutinib PBO, followed by an additional 12 weeks of treatment with open-label abatacept (Section 1.4.2).

1.4.2 Master Protocol: Study Treatment

Blinded treatment assignment will be conducted by randomization on Day 1 and managed by interactive response technology (IRT). Subjects will undergo screening evaluations to determine eligibility within 28 days prior to administration of study medication. After successfully meeting entry criteria and completing screening assessments, subjects in each

Clinical Protocol BMS-986195

sub-protocol will be randomized in a blinded manner to branebrutinib or PBO treatment. Separate randomization schedules will be developed for each sub-protocol. Details of blinding and treatment assignment are provided in Section 6.0 of each sub-protocol. Subjects will be randomized to branebrutinib or PBO as follows:

IM014029

Branebrutinib

- SLE sub-protocol 3:1 ratio of branebrutinib 9 mg to PBO QD
- o pSS sub-protocol 2:1 ratio of branebrutinib 9 mg to PBO QD
- o RA sub-protocol 3:1 ratio of branebrutinib 9 mg to PBO QD
- Randomization in the SLE sub-protocol will be stratified by immunosuppressant use (yes/no).
- Randomization in the pSS sub-protocol will be stratified by hydroxychloroquine (HCQ) use (yes/no).
- No stratification will be imposed in the RA sub-protocol.

1.4.3 Master Protocol: Independent Data Monitoring Committee

Safety monitoring, including laboratory monitoring, will be ongoing throughout the study, for subjects in all treatment arms, along with the employment of an Independent Data Monitoring Committee (DMC). The DMC will conduct at regular, prespecified intervals and on an ad hoc basis if warranted, safety review meetings throughout the study to ensure that the benefit and risks of study participation remain acceptable. Based on the DMC's assessment, recommendations of protocol modifications or other actions may occur, including but not limited to sample size adjustment, study modification, or discontinuation of the study or one or more of the sub-studies. In addition, hold of enrollment, pending more detailed assessment may be requested. For details, please refer to Sections SLE 4.1.1, pSS 4.1.1, and RA 4.1.1.

1.4.4 Master Protocol: Duration of Participation

- The duration of participation in the SLE and pSS sub-protocols will be approximately 32 weeks divided into the following periods: screening (up to 4 weeks [28 days]), double-blind PBO-controlled treatment for 24 weeks (Week 0 to Week 24) and follow-up (4 weeks).
- The duration of participation in the RA sub-protocol will be approximately 32 weeks divided into the following periods: screening (up to 4 weeks), double-blind PBO-controlled treatment for 12 weeks (Week 0 to Week 12), open-label abatacept treatment for an additional 12 weeks (all subjects; Week 12 to Week 24), and follow-up (4 weeks).

1.4.5 Master Protocol: Study Assessments

Efficacy and safety will be assessed throughout the study. Blood samples will be collected for PK and biomarker clinical laboratory assessments.

1.4.6 Master Protocol: Statistical Methods

1.4.6.1 General Methodology

Efficacy, safety, PK, and biomarker data will be combined and summarized across each sub-protocol for variables that are similar among the sub-protocols in addition to analyses provided

Protocol Amendment No.: 04

Clinical Protocol
BMS-986195
IM014029
Branebrutinib

separately for each sub-protocol. Statistical methods will be similar to those specified in the sub-protocols.

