	Continuous endpoints (change from baseline values) will be analyzed using analysis of covariance. The baseline value of the endpoint being tested will be added into the model as a covariate. Treatment differences based on least-squares means and corresponding 2-sided 95% CIs will be provided for the difference between branebrutinib and PBO.
	Supportive Analyses
	Supportive analyses using logistic regression for the primary endpoint may be performed to incorporate additional covariates of interest and to confirm primary analysis results. The odds ratio and the corresponding 95% CI will be provided.
	Supportive analyses for continuous endpoints may be performed using MMRM to investigate response over time.
	Imputation Method
	Nonresponder imputation will be used for binary endpoints for subjects who discontinue study treatment early, start a protocol-prohibited medication/therapy prior to the specified timepoint, or otherwise have missing endpoint data for the specified timepoint. Other imputation methods may be considered for sensitivity analyses and will be described in the SAP if used.
	Testing Strategy for Secondary Endpoints
	There will be no alpha level adjustment for multiple endpoint testing.

SLE 9.4.1.1 Subgroup Analyses

Subgroup analyses will be conducted for the primary and secondary efficacy endpoints on the FAS population. Subgroups that may be evaluated include the following:

• Gender

Clinical Protocol
BMS-986195
IM014029 - SLE
Branebrutinib

- Race
- Tobacco use

Additional subgroups defined for descriptive summaries may be specified in the SAP.

SLE 9.4.2 Safety Analyses

Safety data will be descriptive in nature and will be summarized using the Safety Analysis Set. Data will be summarized using descriptive statistics (n, mean, standard deviation, median, minimum, and maximum), unless otherwise specified, for continuous variables and frequency distributions (counts and percentages) for categorical variables. Safety data will be summarized separately for each sub-protocol and with all sub-protocols combined.

Data will be presented for the following treatments:

- Branebrutinib
- PBO

SLE 9.4.2.1 Adverse Events

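### Combined between-arm summaries should be stratified by sub-protocol: pSS is randomized 2:1 but SLE and RA 3:1, so disease mix differs between the pooled arms

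*Combined protocol and SAP*

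**What the plan says.** Section 1.4.6.1 (General Methodology) plans that "Efficacy, safety, PK, and biomarker data will be combined and summarized across each sub-protocol for variables that are similar among the sub-protocols". This is additional to the analyses by sub-protocol, and the only method given is that it will resemble the sub-protocol methods. For safety, the SLE synopsis, SLE 9.4.2 and the pSS synopsis all say: "Safety data will be summarized separately for each sub-protocol and with all sub-protocols combined". Both synopses describe the adverse-event summary as numbers and percentages of affected subjects, plus event counts, by treatment group.

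On design, Section 1.4.2 says "Separate randomization schedules will be developed for each sub-protocol" and sets the ratios: "SLE sub-protocol 3:1 ratio of branebrutinib 9 mg to PBO QD", "pSS sub-protocol 2:1 ratio of branebrutinib 9 mg to PBO QD" and "RA sub-protocol 3:1 ratio of branebrutinib 9 mg to PBO QD". Section 1.4.1 gives the sizes ("60 subjects in the SLE sub-protocol, 45 subjects in the pSS sub-protocol, and 80 subjects in the RA sub-protocol") and the blinded durations: "For the SLE and pSS sub-protocols, there will be a 24-week double-blind placebo-controlled treatment period", and 12 weeks in RA before open-label abatacept.

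The stratification factor is immunosuppressant use in SLE, hydroxychloroquine use in pSS, and none in RA. The text available here states no sub-protocol stratum or model term, no exposure adjustment and no common time window for the combined summaries. None of these is ruled out.

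**The concern.** Treatment is randomized within each sub-protocol, not across the study. When sub-protocols with different ratios are added together, the two pooled arms no longer hold the same mix of diseases. If event rates or outcome levels differ by disease, the pooled arms then differ even when the drug does nothing.

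The combined safety view is one of the reasons Section 1.2 gives for using a master protocol, and that section also says placebo provides the basis for comparing safety. Readers will therefore compare the pooled columns. Some efficacy measures are also shared: EQ-5D-5L and PROMIS Fatigue in all three sub-protocols, and DAS28-CRP in pSS and RA.

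The pointer to similar methods does not settle the matter. A method written for one disease cannot contain a sub-protocol term, and the stratification factors are not common to the three sub-protocols.

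**Working it through.** **Inputs.** Sizes are from Section 1.4.1, and ratios from Section 1.4.2. Arm size = N × ratio/(ratio + 1) for branebrutinib and N/(ratio + 1) for placebo.

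| | SLE | pSS | RA | Total |
|---|---|---|---|---|
| Randomized | 60 | 45 | 80 | 185 |
| Ratio | 3:1 | 2:1 | 3:1 | |
| Branebrutinib | 45 | 30 | 60 | 135 |
| Placebo | 15 | 15 | 20 | 50 |
| Share of branebrutinib | 33.3% | 22.2% | 44.4% | |
| Share of placebo | 30.0% | 30.0% | 40.0% | |
| Difference (points) | +3.3 | -7.8 | +4.4 | |

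The arms add to 135 + 50 = 185, the planned total. The SLE and pSS arm sizes match those in the sample-size text. The imbalance comes from pSS alone: at 3:1 throughout, the mix would be the same in both arms.

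**Spurious difference with no drug effect.** With event risk r in each disease, the same in both arms, the crude difference is the sum of (share of branebrutinib - share of placebo) × r. In exact fractions this is (3·r_SLE - 7·r_pSS + 4·r_RA)/90. It is negative when the pSS risk exceeds (3·r_SLE + 4·r_RA)/7, and positive when it is below. With risks between 0 and 1 the limit is ±7/90 = ±7.8 points.

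The documents give no event rates by disease, so every risk below is an assumption. Example for 60/70/40%: branebrutinib (27 + 21 + 24)/135 = 53.3%; placebo (9 + 10.5 + 8)/50 = 55.0%; difference -1.7 points.

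| Assumed SLE/pSS/RA risk | Branebrutinib | Placebo | Difference (points) |
|---|---|---|---|
| 50/50/50% | 50.0% | 50.0% | 0.0 |
| 60/60/40% | 51.1% | 52.0% | -0.9 |
| 70/70/45% | 58.9% | 60.0% | -1.1 |
| 60/70/40% | 53.3% | 55.0% | -1.7 |
| 30/60/30% | 36.7% | 39.0% | -2.3 |
| 60/80/40% | 55.6% | 58.0% | -2.4 |
| 50/90/40% | 54.4% | 58.0% | -3.6 |
| 20/80/20% | 33.3% | 38.0% | -4.7 |
| 70/40/45% | 52.2% | 51.0% | +1.2 |
| 60/30/60% | 53.3% | 51.0% | +2.3 |

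**Size against sampling error.** For 60/70/40% the crude standard error is √(0.533 × 0.467/135 + 0.55 × 0.45/50) = 0.082, about 8 points. In the cases where the ratio was computed, the bias was 0 to 0.6 standard errors. In three cases tried (60/70/40%, 30/60/30%, 20/80/20%), the two-sided type I error of a crude z-test was 4.7% to 5.1%. It stays near 5% partly because the crude standard error ignores the strata and is somewhat too large (for example 0.080 against a true 0.077 at 30/60/30%).

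**Duration.** Mean planned blinded exposure is (45 × 24 + 30 × 24 + 60 × 12)/135 = 18.7 weeks on branebrutinib and (15 × 24 + 15 × 24 + 20 × 12)/50 = 19.2 weeks on placebo. With one constant hazard for all diseases and both arms, between 0.01 and 0.10 per week, the shorter RA period shifts the crude difference by -0.5 to -1.1 points.

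**Stratified alternative.** Mantel-Haenszel weights are n_active × n_placebo/N: SLE 45 × 15/60 = 11.25, pSS 30 × 15/45 = 10, RA 60 × 20/80 = 15. With no drug effect each within-disease difference has expectation 0, so the weighted difference does too. The standard error is about the same as the crude one: 0.078 against 0.080 at 30/60/30%, and 0.080 against 0.082 at 60/70/40%.

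**The case against.** The strongest defence is that no inference rests on these tables. They supplement the separate analyses, safety is described as descriptive in SLE 9.4.2, and the results for each disease sit beside the pooled column. The visible primary endpoints (mCLASI response in SLE, the composite in pSS) are disease-specific and would not be pooled. The bias is below one standard error, and a plain pooled percentage is a legitimate display. All of this stands, and it limits the weight of the point.

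A second defence is that crude pooling is never stated. The sub-protocol efficacy methods already use stratified tests or a stratum effect, so similar methods could mean stratifying the combined analysis as well. The SAP is to be finalized before database lock and may say so. The RA sub-protocol, pSS Section 9 and any separate SAP text were not available here. For efficacy this is fair: the plan is silent, and a reader who infers a deliberate choice of crude pooling goes beyond it. For adverse events the described summary is numbers and percentages by arm, and following it literally gives crude pooled arms.

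A third defence concerns the remedy. With placebo strata of 15, 15 and 20, stratified differences for rare preferred terms would rest on many empty cells. That is correct, and the fix is limited accordingly.

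**Conclusion.** The point holds in a limited form. A crude pooled between-arm comparison would be confounded by disease because pSS has a different allocation ratio. Under assumed rates with no drug effect, the spurious difference was -4.7 to +2.3 points in the cases tried, within a limit of ±7.8 and against a standard error of about 8 points. The calculation assumes planned arm sizes and invented disease-specific rates. It concerns only the additional combined summaries.

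Three stronger readings are not supported:

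- A reader might infer that each sub-protocol has its own ratio and blinded duration. Only pSS differs in ratio, and only RA in duration.
- A reader might infer that pooling makes branebrutinib look safer because its arm holds more 12-week RA subjects. Duration alone gives about -0.5 to -1.1 points under equal hazards. The larger negative figures come from assuming high pSS rates, and the sign reverses if pSS rates are low.
- A reader might infer that the trial's conclusions are at risk. The analyses within each sub-protocol are unaffected.

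Stratification is still worth specifying. It analyses the data within the groups that were randomized, removes the mix effect exactly when there is no drug effect, and costs essentially no precision in the cases checked.

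**What to change.** In Section 1.4.6.1 and the SAP, state that any combined between-arm comparison:

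- uses estimates stratified by sub-protocol, meaning Mantel-Haenszel risk differences for binary outcomes and a sub-protocol term in pooled ANCOVA or MMRM;
- is restricted to the blinded placebo-controlled period, which for RA is Weeks 0 to 12;
- is accompanied by exposure-adjusted incidence rates stratified by sub-protocol.

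Crude pooled percentages may remain as description, labelled as unadjusted. Limit stratified differences to overall adverse events, serious adverse events, adverse events of interest and common-event categories, because intervals for rare preferred terms would be unstable. If the SAP or the RA and pSS statistical sections already say this, a cross-reference from Section 1.4.6.1 is enough. The cost is a few sentences and minor programming; design and sample size are unchanged.

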1.4.6.2 Master Protocol: Interim Analysis

An interim analysis will be performed for future study planning at a time point after approximately 50% of the RA subjects have either completed Week 12 efficacy assessments or have discontinued prior to Week 12. The objective of this interim analysis will be to help in early planning for further clinical development of the compound. The study will not be stopped on the basis of any efficacy findings in the interim analysis, and there is no plan to modify the study design based on the results of this interim analysis. The results of this interim analysis will be reviewed by an unblinded development team that is independent of the study team responsible for the conduct of the study. The study team responsible for managing the study, including the Medical Monitors, will remain blinded to treatment assignment and will not have access to any unblinded interim analysis results or data until the study is completed and there is a final database lock and unblinding.

1.4.6.3 Master Protocol: Analysis and Reporting

After all subjects in the RA sub-protocol have completed Week 12 efficacy assessments or discontinued treatment/study prior to Week 12, an analysis of efficacy, safety, PK, and PD will be performed using data up to Week 12. The objective of this analysis will be to support early planning decisions on clinical development of the compound. After all subjects in a sub-protocol have finished the respective sub-protocol and the data have been locked for the sub-protocol, final analyses for that sub-protocol will be performed. Details of these analyses will be described in the statistical analysis plan (SAP).

The study team responsible for managing the study, including Medical Monitors, will remain blinded to treatment assignment and the results of safety analysis until full database lock and treatment unblinding has occurred. The data will be reported only after completion of all 3 sub-protocols.

1.4.7 Master Protocol: Justification for Dose

The selection of the branebrutinib dose and regimen to be assessed in this Master Protocol study was based on findings in the first-in-human (FIH) and nonclinical studies.

In the multiple ascending dose (MAD) panels (Part B) of the FIH study (Study IM014001), healthy subjects received branebrutinib solution once daily QD for 14 days at 4 dose levels (0.3, 1, 3, and 10 mg; n = 6 subjects per dose).³⁷ Increases in maximum observed plasma concentration (Cmax) and area under the plasma concentration-time curve (AUC) from the start to the end of the dosing period (AUC[TAU]) were approximately dose proportional within the dose levels tested. The mean half-life (T-HALF) was shorter than 2 hours across the dose range tested, indicating that branebrutinib was rapidly eliminated from the body. Consequently, as expected, accumulation at steady-state after multiple daily dosing was negligible.

Safety results were similar between branebrutinib 3 mg and 10 mg solution doses in Study IM014001. The drug was well-tolerated at both dose levels and most AEs observed were

similar in subjects receiving PBO and active treatment. The most common AEs included headache and upper respiratory tract infection. Based on the AUC in rats and dogs at the no-adverse-effect-level (NOAEL) after chronic daily administration (rat, 6 months; dog, 9 months), the safety multiple in humans after multiple doses of 10 mg is $> 500 \times .^{12}$ In the current study, the dose level of branebrutinib will be 9 mg; consistent with a good safety margin for humans participating in the study.

The dose for branebrutinib was selected based on the totality of data from multiple biomarkers obtained through post-hoc analysis from Study IM014001. The biomarkers evaluated were BTK occupancy by branebrutinib, inhibition of ex vivo stimulated cluster of differentiation (CD)69 expression, and plasma C-X-C motif chemokine ligand 13 (CXCL13) levels. The maximum occupancy reached \geq 99% at branebrutinib doses of 1 mg and above (100%; maximum occupancy at doses \geq 3 mg); however, the time to reach maximum occupancy was faster and maintained for a longer duration at 3 mg and 10 mg doses (solution formulation). The variability of the effect was lower for the higher dose of 10 mg. A similar result was obtained for CD69 inhibition, while the largest median inhibition in CD69 expression was observed at the branebrutinib 10 mg dose. The highest inhibition of plasma levels of CXCL13 was also obtained at the 10 mg dose level. Considering the higher variability and expression of BTK in patients with immune-mediated disorders, ⁴ the higher dose is expected to sustain more stable inhibition of BTK for optimal chronic treatment of a larger proportion of patients.

The comparison of exposure between the branebrutinib 10 mg solution formulation from Study IM014001 and the branebrutinib 9 mg capsule formulation (3×3 mg) from Day 1 Cycle 2 in Study IM014023 demonstrated comparable exposure for Cmax and AUC(TAU) with only slight delay in time to maximum concentration (Tmax) for capsule formulation. Thus, the use of 3×3 mg capsules of branebrutinib is expected to be equivalent to the 10 mg solution formulation in terms of exposure, safety, and pharmacodynamic (PD) effects.

The exposure for the 9 mg dose level is also much lower than the safety limit for exposure identified in preclinical studies. As previously mentioned, based on the AUC in rats at the NOAEL, the safety multiple in humans after multiple doses of 10 mg is $> 500 \times$.

In summary, the dose to evaluate PD response with optimal safety and best potential to detect an efficacy signal was chosen to be 9 mg branebrutinib administered as 3×3 mg capsules.

All RA subjects will receive open-label treatment with abatacept SC 125 mg administered QW in a prefilled syringe. This dose and regimen is approved for the treatment of patients with active RA and has demonstrated efficacy in Study IM101174 while maintaining steady-state trough concentration (Cminss) of $10 \,\mu\text{g/mL}$ and above, the exposure associated with near-maximal efficacy response in RA, in patients across all body weights.³⁸

